## 2. Medical History and Concurrent Diseases

- a) Infections:
  - i) Active co-infection with
    - (1) Both hepatitis B and C as evidenced by detectable HBV surface antigen or HBV DNA and HCV RNA, OR
    - (2) Hepatitis D infection in subjects with hepatitis B
  - ii) Known history of testing positive for human immunodeficiency virus (HIV) or known acquired immunodeficiency syndrome (AIDS)
  - iii) Active bacterial or fungal infections requiring systemic treatment within 7 days prior to study entry.
- b) Interstitial lung disease that is symptomatic or may interfere with the detection and management of suspected drug-related pulmonary toxicity.
- c) Prior organ allograft or allogeneic bone marrow transplantation
- d) Pre-existing thyroid abnormality with thyroid function that cannot be maintained in the normal range with medication.
- e) Subjects with any active, known, or suspected autoimmune disease.
  - i) Subjects with vitiligo, type 1 diabetes mellitus, resolved childhood asthma or atopy are permitted to enroll.
  - ii) Subjects with suspected autoimmune thyroid disorders may be enrolled if they are currently euthyroid or with residual hypothyroidism requiring only hormone replacement.
- f) Prior malignancy active within the previous 3 years except for locally curable cancers that have been apparently cured, such as basal or squamous cell skin cancer, superficial bladder cancer, or carcinoma in situ of the prostate, cervix, or breast.
- g) Subjects with a condition requiring systemic treatment with either corticosteroids (> 10 mg/day prednisone equivalent) or other immunosuppressive medications within 14 days of study administration. Inhaled or topical steroids and adrenal replacement doses > 10 mg/day prednisone equivalents are permitted in the absence of active autoimmune disease.
- h) Any serious or uncontrolled medical disorder that in the opinion of the investigator may increase the risk associated with study participation or study drug administration, impair the ability of the subject to receive protocol therapy, or interfere with the interpretation of study results.

### **3. Prior and Current Therapies**

- a) Prior treatment with an anti-PD1, anti-PD-L1, anti-PD-L2, anti-CTLA-4 antibody, or any other antibody or drug specifically targeting T-cell co-stimulation or immune checkpoint pathways.
- b) Prior participation in a BMS nivolumab or ipilimumab study.
- c) Radiotherapy within 2 weeks prior to study drug administration and no additional radiotherapy for the same lesion is planned.
- d) Treatment with any chemotherapy, biologics for cancer, or investigational therapy within 28 days of first administration of study treatment, with the exception of sorafenib which requires a 14 day washout period.

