### 3. Prior and Current Therapies

- a) Prior therapy with an anti-PD-1, anti-PD-L1, anti-PD-L2, anti-CD137, or anti-CTLA-4 antibody (or any other antibody or drug specifically targeting T-cell costimulation or checkpoint pathways)

- b) Prior participation in a BMS nivolumab study.
- c) Prior use of systemic investigational agents for HCC.
- d) Treatment with strong CYP3A4 inducers within 7 days of study entry, including rifampin (and its analogues) or St John's wort.
- e) Current therapeutic anticoagulation therapy.
- f) Treatment with anti-platelet therapy (aspirin at dose  $\geq$  300 mg/day, clopidogrel at dose  $\geq$  75 mg/day)
- g) Radiotherapy within 4 weeks prior to start of study drug. Palliative radiotherapy for symptomatic control is acceptable if completed at least 2 weeks prior to study drug administration) and no additional radiotherapy for the same lesion is planned.

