### **7. Other Exclusion Criteria**

- a) Prisoners or subjects who are involuntarily incarcerated
- b) Subjects who are compulsorily detained for treatment of either a psychiatric or physical (eg, infectious disease) illness

Eligibility criteria in this study have been carefully considered to ensure the safety of the study subjects and that the results of the study can be used. It is imperative that subjects fully meet all eligibility criteria.

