### **3.4 Concomitant Treatments**

#### **3.4.1 Prohibited Treatments**

- Locoregional therapy for HCC
- Concurrent antineoplastic therapy, such as chemotherapy, molecular targeted therapy, hormonal therapy, immunotherapy, botanical formulations with an approved indication for cancer treatment (eg traditional Chinese medicines), radiation therapy (except for palliative local therapy described in Section 3.4.1)
- Investigational agents for the treatment of cancer
- For subjects receiving nivolumab, systemic steroids > 10 mg within 14 days of dosing (with a few exceptions eg, steroids for adrenal insufficiency, steroids if taken as part of prophylaxis for CT prep [Section 3.4.2])
- Concurrent immunosuppressive agents (except to treat a drug-related adverse event).
- Medications contraindicated with sorafenib treatment (refer to the package insert, summary of product characteristics (SmPC) or similar document).

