### **3.4.3 Palliative Local Therapy**

Palliative local therapy for clinically symptomatic tumor sites (eg bone pain) including palliative (limited-field) radiation and palliative surgical resection may be considered if the following criteria are met:

- The subject is considered to have progressed at the time of palliative therapy and meets criteria to continue with treatment beyond progression ([Section 3.1.8](#)).
- The lesion for palliative local therapy is a non-target lesion
- The case is discussed with the BMS medical monitor. Palliative therapy must be clearly documented as such in the study record.
- Tumor lesions requiring palliative local therapy should be evaluated for objective evidence of disease progression prior to the initiation of such therapy. In addition, sites must request an Independent Review of Progression from the third party radiology vendor prior to the initiation of palliative local therapy. However, the initiation of palliative local therapy need not be delayed to await the assessment by the Independent Review of Progression.
- Palliative therapy must be clearly documented in the source records and electronic case report form. Details in the source records should include: dates of treatment, anatomical site, dose administered and fractionation schedule, and adverse events.

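### Combination-cohort radiotherapy exclusion 3(c) is inverted as written: it bars recent radiotherapy with none planned, but not recent radiotherapy with more planned to the same lesion

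*Combined protocol and SAP*

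**What the plan says.** Section 3.3.3.2, exclusion 3(c), for the nivolumab plus ipilimumab combination cohort is a single exclusion item: "Radiotherapy within 2 weeks prior to study drug administration and no additional radiotherapy for the same lesion is planned".

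The matching item for the 1L cohort, Section 3.3.2.2, exclusion 3(g), has two parts. The exclusion itself is "Radiotherapy within 4 weeks prior to start of study drug". An exception follows for palliative radiotherapy given for symptoms, which is "acceptable if completed at least 2 weeks prior to study drug administration) and no additional radiotherapy for the same lesion is planned".

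During the study, Section 3.4.1 prohibits "radiation therapy (except for palliative local therapy described in Section 3.4.1"). That cross-reference points back to its own section; palliative local therapy is described in Section 3.4.3. One condition there is: "The subject is considered to have progressed at the time of palliative therapy and meets criteria to continue with treatment beyond progression". The lesion must also be non-target, and the case must be discussed with the medical monitor.

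The eligibility lists are meant to be applied strictly. Section 3.3 allows no exceptions, and the combination-cohort list closes with "It is imperative that subjects fully meet all eligibility criteria".

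**The concern.** In the 1L cohort, the clause about no further radiotherapy to the same lesion helps to let a subject in. In 3(c) almost the same words appear without the part that makes them permissive, so they become half of a condition for keeping a subject out. The clause then works backwards: having more radiotherapy planned takes a recently irradiated subject out of the exclusion.

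At stake is a consistent entry rule. A site that follows the text and a site that guesses the intent would decide differently on the same subject. A subject who enters under the literal text with further radiotherapy planned would also meet a conflict at once with the on-study prohibition. No other combination-cohort eligibility item names planned radiotherapy. Inclusion 2(d) concerns locoregional therapy, which inclusion 2(c)(ii) lists separately from radiotherapy.

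**Working it through.** No sample-size, power or error-rate figure is involved, so the check is one of logic.

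**Inputs.** The text of 3(c) (Section 3.3.3.2) and of 1L 3(g) (Section 3.3.2.2).

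**Notation.** A = radiotherapy within 2 weeks before study drug. P = more radiotherapy planned to the same lesion.

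- 3(c), read literally: exclude if A and not P.
- 1L 3(g): exclude if radiotherapy fell within 4 weeks, unless it was palliative, was completed at least 2 weeks before study drug, and not P.

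Take a subject whose radiotherapy was palliative and fell within the last 4 weeks:

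| Last radiotherapy | More planned, same lesion | 3(c), literal | 1L 3(g) |
|---|---|---|---|
| Within 2 weeks | No | Excluded | Excluded |
| Within 2 weeks | Yes | **Not excluded** | Excluded |
| 2 to 4 weeks ago | No | Not excluded | Accepted |
| 2 to 4 weeks ago | Yes | **Not excluded** | Excluded |

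Under 3(c) one row of four is excluded. In both rows with further radiotherapy planned, the 1L rule excludes and 3(c) does not. Within the 2-week window, 3(c) separates the two kinds of subject in the wrong direction: the one whose radiotherapy is finished is kept out, and the one with more to come is not.

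**Is this an inversion or a choice?** The closing clause is the same in both cohorts. What 3(c) lacks is the wording that makes completed palliative radiotherapy acceptable. The same list has a second reversed item: exclusion 1(c) is phrased as the absence of a history of hepatic encephalopathy, which literally would exclude subjects who never had it. The lists for the other cohorts (Section 3.3.1.2, 2(a); Section 3.3.2.2, 1(c)) state that item in the expected direction. Two reversals in one list point to drafting, not design.

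**The case against.** The strongest reply is that no site would read 3(c) this way. Several exclusion items in this protocol carry permissive or explanatory clauses, the 1L item makes the intent fairly plain, and a literal reading of 1(c) would shut out almost everyone. Other provisions also stand in the way. Inclusion 1(b) requires that subjects be able and willing to meet the study's requirements, and a subject already booked for prohibited radiotherapy hardly does. Sections 3.4.1 and 3.4.3 confine radiotherapy on study to palliative treatment of non-target lesions in subjects considered to have progressed.

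This stands as a limit on practical effect. It does not repair the entry rule: 1(b) does not mention radiotherapy, and 3.4.1 and 3.4.3 govern conduct after entry. If sites apply the intent, they do so against the text of a list that they are told to meet in full.

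A reader might infer more: that subjects let through will be irradiated on study, and so distort the co-primary response rate and the Stage 1 tolerability count. The documents do not support that. It would need a literal reading at entry and then, outside the 3.4.3 exception, a breach of the on-study rules. Inclusion 2(c)(ii) requires a measurable lesion never treated with radiotherapy, which limits the effect on response, though it does not protect every target lesion. One subject is 1/12 = 8.3 percentage points of a Stage 1 arm and 1/40 = 2.5 points of a full arm, but that is the weight of any single subject, not an estimate of bias. Going from 4/12 (33.3%) to 5/12 (41.7%) triggers sponsor review under Sections 3.1.4 and 3.1.5, not closure of the arm.

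**Conclusion.** The point holds as a drafting error in an operative eligibility criterion. Read literally, 3(c) excludes one of the four combinations of recent and planned radiotherapy, and within the 2-week window it bars the subject with none planned while passing the one with more planned to the same lesion. It should be corrected because the criteria are to be met in full.

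Its size beyond that is not known. The documents give no frequency of recent or planned radiotherapy and no sign that any site misapplied the item, so no effect on response rate or tolerability is claimed. Sample size and the planned confidence intervals are untouched.

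The conclusion assumes that an exclusion item joined by *and* applies only when both parts are true. It is confined to further radiotherapy to the same lesion: a recently irradiated subject whose only further treatment is planned for a different lesion is still excluded. A reader might also infer that 3(c) was meant to bar every planned course, including a first course to a new lesion. Neither cohort's clause says that.

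**What to change.** Reconcile 3(c) with 1L exclusion 3(g) and with Sections 3.4.1 and 3.4.3. Restate it so that recent radiotherapy and planned further radiotherapy to the same lesion are two separate conditions, each with its intended direction made explicit. The sponsor should confirm which rule and which window are intended; the documents do not settle that, and this point does not propose one. In the same edit, correct the direction of exclusion 1(c) and the self-reference in Section 3.4.1.

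Then compare enrolled subjects' radiotherapy records with the clarified rule and report the result descriptively. It should not be presented as a list of deviations, because the clarified wording was not in force when those subjects entered.

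The cost is a few lines of protocol text, a matching change to the eligibility checklist and a short records check. No study procedure is added.

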###### **2. Target Population**

- a) Subjects with advanced hepatocellular carcinoma not amenable for management with curative intent by surgery or local therapeutic measures.
- b) Histological confirmation of hepatocellular carcinoma. Subjects with radiological diagnosis may be enrolled for screening in the study but histological confirmation is mandatory prior to initiation of study therapy.
- c) Subjects must fulfill the criteria for prior therapy as follows:
  - i) For the dose escalation cohorts (uninfected, HCV-infected, and HBV-infected), subjects must have progressive disease following or be intolerant of at least one line of systemic therapy or refuse sorafenib treatment (refusal must be documented); subjects cannot be on active cancer therapy during the screening period.
  - ii) For the uninfected sorafenib progressors in the Expansion Phase, subjects must have had documented radiographic or symptomatic progression during or after sorafenib therapy
  - iii) For the uninfected sorafenib naive or intolerant subjects in the Expansion Phase, subjects must either have never received sorafenib treatment or were intolerant to sorafenib therapy as defined in [Section 1.4.9](#).
  - iv) For the HCV and HBV cohorts in the Expansion Phase, subjects must have received sorafenib treatment and be either intolerant or have had documented radiographic or symptomatic progression during or after sorafenib therapy as defined in [Section 1.4.9](#).

- d) Subjects must have Child-Pugh scores as follows ([Appendix 3](#)):
  - i) Dose Escalation Phase: Child-Pugh score of 7 points or less, ie, Child-Pugh A or Child Pugh B7.
  - ii) Expansion Phase: Child-Pugh score of 6 points or less, ie, Child-Pugh A.
- e) Eastern Cooperative Oncology Group (ECOG) Performance Status of 0 to 1 ([Appendix 4](#));
- f) The noninfected HCC arm Dose Escalation Phase and Expansion Phase will include subjects with prior HCV or HBV infection provided there is no active viral replication (negative for HBV DNA and/or HBV surface antigen and HCV RNA). HBV exposed subjects with resolved HBV infection who have seroconverted must have detectable HBsAb and HBcAb titers and have undetectable HBsAg and HBV DNA.
- g) In the Dose Escalation Phase and Expansion Phase, the HCV infected arm must have evidence of HCV RNA. Subjects may have evidence of prior HBV infection but must have detectable HBsAb and HBcAb titers and have undetectable HBsAg and HBV DNA.

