#### **2. Medical History and Concurrent Diseases**

- a) Any history of hepatic encephalopathy
- b) Any prior (within 1 year) or current clinically significant ascites as measured by physical examination and that requires active paracentesis for control
- c) Active coinfection with both hepatitis B and C
- d) Hepatitis D infection in subjects with hepatitis B
- e) Prior malignancy active within the previous 3 years except for locally curable cancers that have been apparently cured, such as basal or squamous cell skin cancer, prostate cancer without evidence of PSA progression or carcinoma in situ such as the following: gastric, prostate, cervix, colon, melanoma, or breast for example.
- f) Subjects with any active autoimmune disease or history of known or suspected autoimmune disease except for subjects with vitiligo, resolved childhood asthma/atopy, type I diabetes mellitus, residual hypothyroidism due to autoimmune condition only requiring hormone replacement, psoriasis not requiring systemic treatment, or conditions not expected to recur in the absence of an external trigger are permitted to enroll.
- g) Uncontrolled or clinically significant cardiac disease
- h) Positive test for human immunodeficiency virus (HIV) or known acquired immunodeficiency syndrome (AIDS)
- i) Known active drug or alcohol abuse
- j) Prior therapy with an anti-PD-1, anti-PD-L1, anti-PD-L2, anti-CD137, or anti-CTLA-4 antibody (or any other antibody or drug specifically targeting T-cell costimulation or checkpoint pathways)
- k) Prior organ allograft or allogeneic bone marrow transplantation
- l) All toxicities attributed to prior anti-cancer therapy other than neuropathy, alopecia and fatigue must have resolved to Grade 1 (NCI CTCAE version 4) or baseline before administration of study drug. Subjects with toxicities attributed to prior anti-cancer therapy which are not expected to resolve and result in long lasting sequelae are permitted to enroll. Neuropathy must have resolved to Grade 2 (NCI CTCAE version 4).
- m) Active bacterial or fungal infections requiring systemic treatment within 7 days
- n) Use of other investigational drugs (drugs not marketed for any indication) within 28 days or at least 5 half-lives (whichever is longer) before study drug administration

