###### **2. Target Population**

- a) Subjects with advanced hepatocellular carcinoma
  - i) disease not eligible for surgical and/or locoregional therapies

- ii) progressive disease after surgical and /or locoregional therapies
- b) No prior systemic therapy for hepatocellular carcinoma.
- c) Histologic confirmation of hepatocellular carcinoma.
- i) Subjects with only a radiologic diagnosis of HCC may be enrolled for screening in the study but histological confirmation is mandatory prior to the start of study therapy.
- ii) Evaluable tumor tissue (formalin-fixed, paraffin embedded archival or recent acquisition) must be received by the central vendor (1 block or 15 unstained slides) for correlative studies prior to randomizing a study subject. If archived samples are not available, subjects must consent to a pre-treatment fresh biopsy as a condition of protocol participation. (Note: Fine needle aspiration (FNA) and bone metastases samples are not acceptable for submission).
- d) At least one RECIST 1.1 measurable untreated lesion. All subjects must have at least one previously untreated, unidimensionally measurable lesion by contrast-enhanced spiral computed tomography (CT)  $\geq 10$  mm or contrast enhanced dynamic magnetic resonance imaging (MRI) scan  $\geq 10$  mm (malignant lymph nodes must be  $\geq 15$  mm on short axis) (additional details are included in [Appendix 2](#))
  - i) The lesion can be accurately measured uni-dimensionally according to RECIST 1.1 criteria
  - ii) The lesion has not been previously treated with surgery, radiotherapy, and/or locoregional therapy (eg: radiofrequency ablation [RFA], percutaneous ethanol [PEI] or acetic acid injection [PAI], cryoablation, high-intensity focused ultrasound [HIFU], transarterial chemoembolization [TACE], transarterial embolization [TAI], etc.)
- e) Locoregional therapy for HCC must be completed at least 4 weeks prior to the baseline scan. All acute toxic effects of any prior local treatment must have resolved to National Cancer Institute (NCI) Common Terminology Criteria for Adverse Events (CTCAE) version 4.0 Grade  $\leq 1$ .
- f) Cirrhotic status of Child-Pugh Class A ([Appendix 3](#))
- g) Eastern Cooperative Oncology Group (ECOG) Performance Status of 0 to 1 ([Appendix 4](#))
- h) Subjects are eligible to enroll if they have non-viral-HCC or if they have HBV-, or HCV-HCC, defined as follows:

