## 2. Target Population

- a) Subjects with advanced hepatocellular carcinoma
  - i) Disease not eligible for surgical and/or locoregional therapies
  - ii) Documented radiographic progression during or after sorafenib therapy or sorafenib intolerance as defined in [Section 1.4.9](#).
- b) Histologic confirmation of hepatocellular carcinoma.
  - i) Subjects with only a radiologic diagnosis of HCC may be enrolled for screening in the study but histological confirmation is mandatory prior to the start of study therapy.
  - ii) Evaluable tumor tissue (formalin-fixed, paraffin embedded archival or recent acquisition) must be received by the central vendor (1 block or 15 unstained slides) for correlative studies prior to randomizing a study subject. If archived samples are not available, subjects must consent to a pre-treatment fresh biopsy as a condition of protocol participation. (Note: Fine needle aspiration (FNA) and bone metastases samples are not acceptable for submission).
- c) At least one RECIST 1.1 measurable untreated lesion. All subjects must have at least one previously untreated, unidimensionally measurable lesion by contrast-enhanced spiral computed tomography (CT)  $\geq 10$  mm or contrast enhanced dynamic magnetic resonance imaging (MRI) scan  $\geq 10$  mm (malignant lymph nodes must be  $\geq 15$  mm on short axis).
  - i) The lesion can be accurately measured uni-dimensionally according to RECIST 1.1 criteria
  - ii) The lesion has not been previously treated with surgery, radiotherapy, and/or locoregional therapy (eg: radiofrequency ablation [RFA], percutaneous ethanol [PEI] or acetic acid injection [PAI], cryoablation, high-intensity focused ultrasound [HIFU], transarterial chemoembolization [TACE], transarterial embolization [TAI], etc.)
- d) Locoregional therapy for HCC must be completed at least 4 weeks prior to the baseline scan. All acute toxic effects of any prior local treatment must have resolved to National Cancer Institute (NCI) Common Terminology Criteria for Adverse Events (CTCAE) version 4.03 Grade  $\leq 1$ .
- e) Cirrhotic status of Child-Pugh Class A (A5 or A6) ([Appendix 3](#))
- f) Eastern Cooperative Oncology Group (ECOG) Performance Status of 0 to 1 ([Appendix 4](#))
- g) Subjects are eligible to enroll if they have non-viral-HCC or if they have HBV-, or HCV-HCC, defined as follows:

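### The combination cohort sets a 14-day sorafenib washout but no rule that sorafenib toxicity must resolve before the first dose; the remaining gap is mainly persistent Grade 2 non-laboratory toxicity such as diarrhea

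*Combined protocol and SAP*

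**What the plan says.** Section 3.3.3.1, inclusion 2.a.ii, defines the combination cohort by its sorafenib history: "Documented radiographic progression during or after sorafenib therapy or sorafenib intolerance as defined in" Section 1.4.9. Section 3.3.3.2, exclusion 3.d, asks for 28 days off chemotherapy, biologics or investigational agents, "with the exception of sorafenib which requires a 14 day washout period".

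The one toxicity-resolution rule in Section 3.3.3 is in inclusion 2.d: "All acute toxic effects of any prior local treatment must have resolved to" Grade 1 or lower. It concerns local treatment only.

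Section 3.3.1.2, exclusion 2.l, for the Dose Escalation and Expansion cohorts, is wider: "All toxicities attributed to prior anti-cancer therapy other than neuropathy, alopecia and fatigue must have resolved to Grade 1" or baseline before study drug. Neuropathy may remain at Grade 2, and long-lasting toxicities not expected to resolve are tolerated.

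**The concern.** The local-treatment sentence in 3.3.3.1 also stands in the 1L cohort (3.3.2.1, inclusion 2.e), differing only in the CTCAE version. It is sufficient there, because 1L subjects have "No prior systemic therapy for hepatocellular carcinoma". In the combination cohort, the therapy that all subjects have had falls outside it.

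Sorafenib-pretreated subjects are therefore protected by a resolution rule when they receive nivolumab alone, but not when they receive the combination. Section 1.4.4 states that most adverse events are more frequent and more severe with the combination. The sections read give no reason for the difference. What is at stake is the subject's condition at the first dose, and how clearly a new gastrointestinal event can be recognised and managed afterwards.

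**Working it through.** No figure in the plan depends on this rule, so there is nothing to recompute. The check sets the eligibility and dosing sections side by side.

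**1. The three eligibility sections.**

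| | Dose Escalation and Expansion (3.3.1) | 1L (3.3.2) | Combination (3.3.3) |
|---|---|---|---|
| Prior sorafenib | Permitted; required in some Expansion cohorts | None | Required of all |
| Sorafenib washout | No fixed interval | Not applicable | 14 days |
| Toxicity resolution | Any prior anti-cancer therapy, to Grade 1 or baseline, with exceptions | Local treatment, to Grade 1 or lower | Local treatment, to Grade 1 or lower |

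On the washout entry for 3.3.1: exclusion 2.n reads "Use of other investigational drugs (drugs not marketed for any indication) within 28 days" or five half-lives, so it does not reach marketed sorafenib. The condition that "subjects cannot be on active cancer therapy during the screening period" belongs to the dose escalation cohorts only. Section 3.3.3 is thus the only one of the three whose toxicity rule leaves out a therapy that all its subjects must have had.

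**2. What other criteria already cover in the combination cohort.**

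- Laboratory toxicity: inclusion 2.h in 3.3.3.1 sets numerical limits on blood counts, coagulation, albumin, bilirubin, transaminases and creatinine clearance. They must be met within 14 days before randomization and without continuous support.
- Severe toxicity: exclusion 2.h in 3.3.3.2 lets the investigator exclude serious or uncontrolled conditions, including those that may "impair the ability of the subject to receive protocol therapy, or interfere with the interpretation of study results". It is a matter of opinion and names no grade, but ongoing Grade 3 diarrhea would probably fall under it.
- Recording: Section 1.4.9 has sorafenib toxicity entered in the medical history, with no threshold.

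**3. What is left.** Section 1.1.5 lists the common sorafenib events: diarrhea (25%), hand-foot skin reaction (24%), fatigue (14%), rash (12%), anorexia (9%), hypertension (7%) and alopecia (7%). Fatigue and alopecia are exempt under exclusion 2.l in any case. For skin events, the on-study hold starts only at Grade 3 (Section 4.1.11). The residue is chiefly diarrhea, anorexia and hypertension persisting at Grade 2. The percentages describe sorafenib use in practice, not toxicity remaining 14 days after stopping, so they do not measure the gap.

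**4. Entry compared with the on-study rules, for Grade 2 diarrhea.**

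- On study, if drug-related: both drugs are held (Section 4.1.11).
- Restart: the general rule is Grade 1 or baseline, but Section 4.1.17 names diarrhea as an exception that must return to baseline.
- At entry, if left over from sorafenib: no fixed limit.

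If baseline means the subject's state at study entry (an assumption; these sections do not define it), unresolved Grade 2 diarrhea also becomes the level at which dosing may restart. The restart rule is then weakest in the subjects who entered with symptoms.

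**The case against.** The strongest reply is that the gap is narrow. Laboratory limits bound the hepatic, hematologic, renal and coagulation toxicity that matters most in this disease, the washout allows recovery, and exclusion 2.h is a backstop. All of this stands, and it confines the point to persistent Grade 2 non-laboratory toxicity.

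Second, the on-study hold is for events caused by nivolumab or ipilimumab. Section 1.1.6 says sorafenib and nivolumab events differ in mechanism and management, so equal grade does not mean equal risk. This stands too: the comparison shows an unmatched rule, not a measured hazard. The same section notes that both drugs produce skin and gastrointestinal signs that need different handling, which is a reason not to begin with one unresolved.

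Third, 3.3.1 uses a resolution rule without a fixed washout and 3.3.3 the reverse, so each might be thought to use one tool. But a fixed interval does not ensure recovery.

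Four stronger readings are tempting and are not supported:

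- That intolerant subjects enter with active toxicity by definition. Section 1.4.9 describes events that persisted or recurred after a break of at least 7 days and a dose reduction. It does not describe a subject 14 days after stopping.
- That nothing protects these subjects. Inclusion 2.h and exclusion 2.h do so in part.
- That carried-over toxicity distorts the Stage 1 tolerability decision or the safety endpoint. The documents give no rate of residual toxicity and no planned share of intolerant subjects, so no such effect can be shown.
- That 14 days is too short. Nothing in the documents bears on this.

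**Conclusion.** The point holds in limited form. Section 3.3.3 has no fixed rule that toxicity from sorafenib, or from other prior systemic therapy, must resolve before the first combination dose. After the existing safeguards are counted, what is exposed is mainly persistent Grade 2 non-laboratory toxicity, with diarrhea the clearest case. A rule would apply to all of the up to 120 subjects but would change entry only for those still above Grade 1 on a non-exempt toxicity. That number is unknown and probably small.

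The patient-safety weight is modest, and the change is worth making because it is cheap. One limit remains: the text available for this review stops at the start of Table 5.1-3, the screening table for this cohort, so a note there cannot be excluded. Section 3.3.3 itself was read in full.

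**What to change.** Keep the 14-day washout. Add to 3.3.3.2 that toxicities attributed to prior systemic anti-cancer therapy, including sorafenib, must have resolved to Grade 1 before the first dose. Carry over the exceptions from 3.3.1.2, exclusion 2.l: alopecia, fatigue, neuropathy up to Grade 2, and long-lasting toxicities not expected to resolve. If enrolment is a worry, Grade 2 skin toxicity could also be allowed, in line with the on-study hold at Grade 3.

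Do not carry over the alternative of return to baseline. An entry baseline would make the rule circular, and no section read requires the grade before sorafenib to be recorded.

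The cost is one eligibility line and a few subjects who start later or are not enrolled. The sample size, the Stage 1 rule and the analyses do not change.
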